10.1.7 Source documents

- Source documents provide evidence for the existence of the participant and substantiate the integrity of the data collected. Source documents are filed at the Investigator's site.
- Data entered in the e-CRF that are transcribed from source documents must be consistent with the source documents, or the discrepancies must be explained. The Investigator may need to request previous medical records or transfer records, depending on the study. Also, current medical records must be available.
- Definition of what constitutes source data can be found in [Section 10.1.8](#).
- The Investigator must maintain accurate documentation (source data) that supports the information entered in the e-CRF.

- Study monitors will perform ongoing source data verification to confirm that data entered into the e-CRF by authorized site personnel are accurate, complete, and verifiable from source documents; that the safety and rights of participants are being protected; and that the study is being conducted in accordance with the currently approved protocol and any other study agreements, ICH-GCP, and all applicable regulatory requirements.

10.1.8 Definition of source data

Source data is all information in original records and certified copies of original records of clinical findings, observations, or other activities in a clinical study necessary for the reconstruction and evaluation of the study. Source data are contained in source documents. Source documents are original documents, data and records such as hospital records, clinic and office charts, laboratory notes, memoranda, pharmacy dispensing records, recorded data from automated instruments, etc.

All the data collected in the e-CRF should be transcribed directly from source documents. Data collected from the study-associated laboratories, endoscopy, CT scan, and patient diary will be considered source data.

10.1.9 Study and site start and closure

First act of recruitment

The study start date is the date on which the clinical study will be open for recruitment of participants.

The first act of recruitment is the first site open and will be the study start date.

Study/Site termination

The Sponsor or designee reserves the right to close the study site or terminate the study at any time for any reason at the sole discretion of the Sponsor. Study sites will be closed upon study completion. A study site is considered closed when all required documents and study supplies have been collected and a study site closure visit has been performed.

The Investigator may initiate study site closure at any time, provided there is reasonable cause and sufficient notice is given in advance of the intended termination.

Reasons for study termination by the Sponsor, as well as reasons for the early closure of a study site by the Sponsor or Investigator, may include but are not limited to:

- For study termination:
 - Information on the product leads to doubt as to the benefit/risk ratio
 - Discontinuation of further study intervention development
- For site termination:

- Failure of the Investigator to comply with the protocol, the requirements of the IRB or local health authorities, the Sponsor's procedures, or GCP guidelines
- Inadequate or no recruitment (evaluated after a reasonable amount of time) of participants by the Investigator
- Total number of participants included earlier than expected

If the study is prematurely terminated or suspended, the Sponsor shall promptly inform the Investigators, the IRBs, the regulatory authorities, and any contract research organization(s) used in the study of the reason for termination or suspension, as specified by the applicable regulatory requirements. The Investigator shall promptly inform the participant and should assure appropriate participant therapy and/or follow-up.

10.1.10 Publication policy

- The results of this study may be published or presented at scientific meetings. If this is foreseen, the Investigator agrees to submit all manuscripts or abstracts to the Sponsor before submission. This allows the Sponsor to protect proprietary information and to provide comments.
- The Sponsor will comply with the requirements for publication of study results. In accordance with standard editorial and ethical practice, the Sponsor will generally support publication of multicenter studies only in their entirety and not as individual site data. In this case, a coordinating Investigator will be designated by mutual agreement.
- Authorship will be determined by mutual agreement and in line with International Committee of Medical Journal Editors authorship requirements.

10.2 APPENDIX 2: CLINICAL LABORATORY TESTS

- The tests detailed in [Table 6](#) will be performed by the local laboratories.
- Protocol-specific requirements for inclusion or exclusion of participants are detailed in [Section 5](#) of the protocol.
- Additional tests may be performed at any time during the study as determined necessary by the Investigator.

Table 6 - Protocol-required laboratory tests

Laboratory tests	Parameters
Hematology	Platelet count RBC count Hemoglobin Hematocrit Total WBC count with differential: Neutrophils Lymphocytes Monocytes Eosinophils Basophils
Clinical chemistry ^a	BUN Creatinine Glucose (Indicate if fasting, or nonfasting) Uric acid Total cholesterol Total protein Albumin Total bilirubin (in case of values above the normal range, differentiation in conjugated and nonconjugated bilirubin) ALT/SGPT AST/SGOT Alkaline phosphatase ^b Lactate dehydrogenase Sodium Potassium Chloride Creatine phosphokinase
Routine urinalysis	
 • Specific gravity • pH, glucose, protein, blood, ketones, urobilinogen, nitrite by dipstick • Microscopic examination (if blood or protein is abnormal)
Pregnancy testing	
 • Serum and urine hCG pregnancy test (as needed for women of childbearing)

Laboratory tests	Parameters
Other screening tests	
potential)
 
 • Serology: 
 - HBsAg, HBcAb or HBcAb IgM and total^c - HBsAb - HCVAb^d - HIV screen (anti-HIV-1 and HIV-2 antibodies) - TB blood testing (IGRA)^e

Abbreviations: ALT: alanine aminotransferase; AST: aspartate aminotransferase; BUN: blood urea nitrogen; HBcAb: hepatitis B core antibody; HBsAb: hepatitis B surface antibody; HBsAg: hepatitis B surface antigen; HBV: hepatitis B; hCG: human chorionic gonadotropin; HCVAb: hepatitis C virus antibody; HIV: human immunodeficiency virus; IgM: immunoglobulin M; IGRA: interferon-gamma release assay; RBC: red blood cell, SAE: serious adverse event; SGOT: serum glutamic-oxaloacetic transaminase; SGPT: Serum glutamic-pyruvic transaminase; TB: tuberculosis; WBC: white blood cell.

NOTES :

- a Details of liver chemistry stopping criteria and required actions and follow-up are given in [Section 7.1.2](#) and Appendix 5 ([Section 10.5](#)). All events of ALT or bilirubin which may indicate severe liver injury (possible Hy's Law) must be reported as an SAE.
- b If alkaline phosphatase is elevated, consider fractionating.
- c In case of results showing HBsAg (negative), and HBcAb total or HBcAb IgM (positive), an HBV DNA testing will be performed and should be confirmed prior to enrollment. Participants who are HBcAb (positive) and HBV DNA (negative) at Visit 1 will require HBV DNA monitoring at Visits 6, 7, and 8 and at the participant's last visit (refer to SoA [[Section 1.3](#)]).
- d In case of results showing HCV Ab (positive), HCV RNA testing will be performed and should be confirmed prior to enrollment.
- e An IGRA is required only for participants without history of active/latent TB.

Investigators must document their review of each laboratory safety report.

10.3 APPENDIX 3: AES AND SAES: DEFINITIONS AND PROCEDURES FOR RECORDING, EVALUATING, FOLLOW-UP, AND REPORTING

10.3.1 Definition of AE

AE definition

- An AE is any untoward medical occurrence in a participant or clinical study participant, temporally associated with the use of study intervention, whether or not considered related to the study intervention.
- NOTE: An AE can therefore be any unfavorable and unintended sign (including an abnormal laboratory finding), symptom, or disease (new or exacerbated) temporally associated with the use of study intervention.

Definition of unsolicited and solicited AE

- An unsolicited AE is an AE that was not solicited using a participant diary and that is communicated by a participant, participant's parent, or LAR who has signed the informed consent. Unsolicited AEs include serious and nonserious AEs.
- Potential unsolicited AEs may be medically attended (ie, symptoms or illnesses requiring hospitalization, or emergency room visit, or visit to/by a health care provider). The participant, participant's parent, or LAR will be instructed to contact the site as soon as possible to report medically attended event(s), as well as any events that, though not medically attended, are of participant, participant's parent, or LAR's concern. Detailed information about reported unsolicited AEs will be collected by qualified site personnel and documented in the participant's records.
- Unsolicited AEs that are not medically attended nor perceived as a concern by participant, participant's parent, or LAR will be collected during interview with the participant, participant's parent, or LAR and by review of available medical records at the next visit.
- Solicited AEs are predefined local and systemic events for which the participant is specifically questioned, and which are noted by the participants in their diary.

Events meeting the AE definition

- Any abnormal laboratory test results (hematology, clinical chemistry, or urinalysis) or other safety assessments (eg, ECG, radiological scans, vital sign measurements), including those that worsen from baseline, considered clinically significant in the medical and scientific judgment of the Investigator (ie, not related to progression of underlying disease), eg:
 - Symptomatic, and/or
 - Requiring either corrective treatment or consultation, and/or
 - Leading to IMP discontinuation or modification of dosing, and/or
 - Fulfilling a seriousness criterion, and/or

- Defined as an AESI.
- Exacerbation of a chronic or intermittent pre-existing condition including either an increase in frequency and/or intensity of the condition.
- New conditions detected or diagnosed after study intervention administration even though it may have been present before the start of the study.
- Signs, symptoms, or the clinical sequelae of a suspected drug-drug interaction.
- Signs, symptoms, or the clinical sequelae of a suspected overdose of either study intervention or a concomitant medication.
- "Lack of efficacy" or "failure of expected pharmacological action" per se will not be reported as an AE or SAE. Such instances will be captured in the efficacy assessments. However, the signs, symptoms, and/or clinical sequelae resulting from lack of efficacy will be reported as AE or SAE if they fulfill the definition of an AE or SAE.
- The signs, symptoms, and/or clinical sequelae resulting from lack of efficacy will be reported as AE or SAE if they fulfill the definition of an AE or SAE. Also, "lack of efficacy" or "failure of expected pharmacological action" also constitutes an AE or SAE.

Events NOT meeting the AE definition

- Any clinically significant abnormal laboratory findings or other abnormal safety assessments which are associated with the underlying disease, unless judged by the Investigator to be more severe than expected for the participant's condition.
- The disease/disorder being studied or expected progression, signs, or symptoms of the disease/disorder being studied, unless more severe than expected for the participant's condition.
- Medical or surgical procedure (eg, endoscopy, appendectomy): the condition that leads to the procedure is the AE.
- Situations in which an untoward medical occurrence did not occur (social and/or convenience admission to a hospital).
- Anticipated day-to-day fluctuations of pre-existing disease(s) or condition(s) present or detected at the start of the study that do not worsen.

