3 OBJECTIVES AND ENDPOINTS

Table 1 - Objectives and endpoints

Objectives	Endpoints
Primary	

 To assess the efficacy of 24-week treatment with dupilumab 300 mg every 2 weeks (q2w) to reduce nasal polyp score (NPS) in participants with chronic rhinosinusitis with nasal polyposis (CRSwNP) who do not use concomitant intranasal corticosteroid (INCS) 	
 Proportion of participants with NPS improvement from baseline ≥ 1 at Week 24
Secondary	

 To assess the efficacy of 24-week treatment with dupilumab 300 mg q2w on other efficacy endpoints in participants with CRSwNP who do not use concomitant INCS 	
Key secondary efficacy endpoints:
 
 Change from baseline to Week 24 in bilateral NPS Change from baseline to Week 24 in nasal congestion/obstruction (NC) symptom severity score using the CRSwNP nasal symptom diary Change from baseline to Week 24 in opacification of sinuses assessed by computerized tomography (CT) scan using the Lund Mackay (LMK) score 
Other secondary efficacy endpoints:
 
 Change from baseline to Week 24: 
 Total symptom score (TSS), a composite score derived from the nasal symptom diary (includes nasal congestion, loss of sense of smell, anterior and posterior rhinorrhea) Loss of smell symptom severity score using the nasal symptom diary Visual analogue scale for rhinosinusitis

 To evaluate the safety of 24-week treatment with dupilumab in participants with CRSwNP 	
 Incidence of treatment-emergent adverse events (TEAEs), treatment-emergent serious adverse events (TESAEs), and TEAEs leading to treatment discontinuation
Tertiary/exploratory	

 To assess the efficacy of 52-week treatment with dupilumab under different dosing regimens to participants with CRSwNP who do not use concomitant INCS 	
 Proportion of participants with NPS improvement from baseline ≥ 1 at Week 52 Change from baseline to Week 52 in bilateral NPS Change from baseline to Week 52 in NC symptom severity score using the CRSwNP nasal symptom diary Change from baseline to Week 52 in opacification of sinuses assessed by CT scan using the LMK score Change from baseline to Week 52 in TSS

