9.3.5 Safety analysis

All safety analyses up to Week 24 will be analyzed for the SAF. Safety data collected during the extension term after Week 24 up to Week 52 will be reported for the SAFE. Safety analyses for the extension term will be presented by dose regimen group and overall.

The number and percentage of participants with at least 1 treatment-emergent AE (TEAE), treatment-emergent serious AE (TESAE), and TEAE leading to treatment discontinuation will be tabulated. Multiple occurrences of the same event in the same participant will be counted once in the tables. The denominator for computing percentages will be the safety populations. Serious AEs and AEs leading to withdrawal from the withdrawal that occur before or after the "treatment-emergent period" will be summarized separately. Definitions for AESI and the method to identify AESIs will be specified in the SAP.

Descriptive statistics of values and change from baseline values for each laboratory and vital signs parameters will be summarized at each time point. The number and percentage of participants with at least 1 incidence of potentially clinically significant abnormality (PCSA) at any time during the treatment-emergent period will be summarized.

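### Protocol 10.3.1 gives two opposite rules on whether lack of efficacy is itself an adverse event, and neither the protocol nor the SAP says which applies

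*Protocol*

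**What the plan says.** Protocol 10.3.1, in its list of events that meet the AE definition, deals with lack of efficacy in two consecutive bullets. The first says that lack of efficacy, or failure of the drug to act as expected, "per se will not be reported as an AE or SAE. Such instances will be captured in the efficacy assessments". The second ends by saying that the same thing "also constitutes an AE or SAE". Both carry the same statement on consequences: "clinical sequelae resulting from lack of efficacy will be reported as AE or SAE if they fulfill the definition of an AE or SAE". The separate list of events that do not meet the definition contains a related exclusion: "The disease/disorder being studied or expected progression, signs, or symptoms of the disease/disorder being studied, unless more severe than expected for the participant's condition". It does not mention lack of efficacy.

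The endpoint that draws on this definition is in Protocol Section 3: "Incidence of treatment-emergent adverse events (TEAEs), treatment-emergent serious adverse events (TESAEs), and TEAEs leading to treatment discontinuation". It is secondary at 24 weeks and exploratory at 52 weeks. Protocol 9.3.5 counts participants with at least one event and adds: "Multiple occurrences of the same event in the same participant will be counted once in the tables". SAP 4.7.2 sorts AEs by timing and tabulates them as reported. It has no rule to include or exclude lack-of-efficacy events.

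**The concern.** An investigator cannot follow both bullets. A participant who does not benefit and has no reportable sequelae yields no AE under the first and an AE under the second. The study is multicenter, so sites may settle the conflict in different ways, and the reported incidence would then partly reflect how each site read the definition.

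The category of TEAEs leading to discontinuation is the most exposed. Protocol 9.3.3 and SAP 4.4.1.2 both expect some participants to stop treatment for lack of efficacy. Under the second bullet such a stop can count as an AE discontinuation; under the first it cannot. The study has one arm, so no concurrent control group carries the same ambiguity and would let a reader judge its effect.

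**Working it through.** **Is there a real conflict?** Setting the two bullets side by side:

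| Question | First bullet | Second bullet |
|---|---|---|
| Signs, symptoms and sequelae of lack of efficacy | Reported if they meet the definition | Reported if they meet the definition |
| Lack of efficacy itself | Not reported; left to the efficacy assessments | Is an AE or SAE |
| Condition for using the bullet (study type, product type) | None | None |

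They differ only in the second row, and there no reading satisfies both.

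**Is it resolved elsewhere?** Protocol 9.3.5 and 9.3.5.1 count AEs as reported, and so does SAP 4.7.2. SAP Appendix 2 (changes to protocol-planned analyses) lists nothing on this point. Protocol Appendix 14 records no amendments, so both bullets are current text.

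**Size.** The plan states no figure to reproduce. Inputs:

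- N = about 25 (Protocol synopsis and 6.1).
- b = share of participants with any other TEAE. Not in the documents; assumed 30% to 70%.
- L = share with a reportable lack of efficacy. Not in the documents; assumed 5% to 38%. The upper value is 1 − 0.620 = 0.38, from the 62.0% responder rate quoted in Protocol 9.1 for the pivotal study. It treats every nonresponder as a lack-of-efficacy case.

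One participant: 1/25 = 4 percentage points.

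Any TEAE changes only for participants with no other TEAE. If the two occur independently, moving from the first rule to the second at all sites raises the incidence by (1 − b) × L:

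| b | L | Increase | Participants of 25 |
|---|---|---|---|
| 70% | 5% | 0.30 × 0.05 = 1.5 points | 0.4 |
| 50% | 10% | 0.50 × 0.10 = 5.0 points | 1.25 |
| 30% | 38% | 0.70 × 0.38 = 26.6 points | 6.7 |

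For TEAEs leading to discontinuation the factor (1 − b) does not apply. A stop for lack of efficacy that is counted as an AE adds 4 points even if the participant had other TEAEs that did not lead to stopping. The documents do not say how many such stops are expected. In the extension-term tables by dose regimen group (Protocol 9.3.5), each group's denominator is smaller than the total, so one participant weighs more.

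**The case against.** A reader might infer that under the second bullet every nonresponder becomes an AE case, so that TEAE incidence could rise by 38 points, or 25 × 0.38 = 9.5 participants. The documents do not support that. Nonresponse is an analysis category derived from centrally read endoscopy (Protocol 8.1.1), and Protocol 9.3.2 also places in it anyone with missing Week 24 data and, from that time on, anyone given systemic corticosteroids for any reason. AEs come from participants' reports and investigators' judgment (Protocol 8.3 and 8.3.2). Nothing links the two. The figure also needs every such participant to have no other TEAE.

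The disputed area is narrow. Surgery during the intervention period already calls for an AE or SAE page (Protocol 6.8.1). Exacerbation of a pre-existing condition is already an AE under 10.3.1, and the exclusion for expected disease progression limits what would be reported. That exclusion is not a further contradiction. The effect on serious TEAEs should be smaller still, because a seriousness criterion in 10.3.2 must be met. All of this stands.

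Any effect would also be partly visible. SAP Table 8 tabulates TEAEs, and TEAEs leading to discontinuation, down to preferred term. SAP 4.2 reports the main reason for stopping treatment. No test or decision threshold is attached to TEAE incidence. This lowers the stakes but does not remove the problem: the tables show lack-of-efficacy events that were reported, not those that a site following the first bullet left out.

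A reader might also infer that the first bullet is the intended rule and that the second bullet's last sentence should simply be deleted. Its reference to the efficacy assessments makes this plausible, but nothing in the documents shows which rule the sponsor meant.

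**Conclusion.** The AE definition is wrong as written. Two consecutive bullets contradict each other on lack of efficacy itself, and nothing else in the protocol or SAP decides between them. Counts for a named secondary endpoint can therefore differ by site for reasons unrelated to safety. The primary endpoint does not use the AE definition.

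The contradiction rests on the text and needs no assumption. The only size that follows from the documents is 4 points per reclassified participant, taking 25 as the denominator. The range of about 1.5 to 27 points for any TEAE rests on the assumed values of b and L and on independence. Its upper end is an outer bound, not an estimate.

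**What to change.** 1. **Protocol 10.3.1.** The sponsor reconciles the two bullets into one rule for all sites and reminds sites of it. Which rule is kept is the sponsor's decision.
2. **SAP 4.7.2.** Add one line: incidences of TEAEs, serious TEAEs and TEAEs leading to discontinuation are shown with and without events that denote only lack of efficacy, and no reported event is dropped. Excluding those preferred terms outright would remove investigator-reported events that the current text allows. The figure without them does not depend on which bullet a site followed. If sites have reported differently, the figure with them may be too low a count under the second rule, and the report should say so.

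The cost is a short protocol clarification through the usual review (Protocol 10.1.1 requires IRB approval of amendments, and health authority approval of substantial ones), a note to sites, and one extra row per table. If data have already been collected, the SAP line is the more useful half.

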10.3.2 Definition of SAE

An SAE is defined as any AE that, at any dose:

- a) Results in death**
- b) Is life-threatening**

The term "life-threatening" in the definition of "serious" refers to an event in which the participant was at risk of death at the time of the event. It does not refer to an event, which hypothetically might have caused death, if it were more severe.

- c) Requires inpatient hospitalization or prolongation of existing hospitalization**

In general, hospitalization signifies that the participant has been admitted (usually involving at least an overnight stay) at the hospital or emergency ward for observation and/or treatment that would not have been appropriate in the physician's office or outpatient setting. Complications that occur during hospitalization are AEs. If a complication prolongs hospitalization or fulfills any other serious criteria, the event is serious. When in doubt as to whether "hospitalization" occurred or was necessary, the AE should be considered serious.

Hospitalization for elective treatment of a pre-existing condition that did not worsen from baseline is not considered an AE.

d) Results in persistent or significant disability/incapacity

- The term disability means a substantial disruption of a person's ability to conduct normal life functions.
- This definition is not intended to include experiences of relatively minor medical significance such as uncomplicated headache, nausea, vomiting, diarrhea, influenza, and accidental trauma (eg, sprained ankle) that may interfere with or prevent everyday life functions but do not constitute a substantial disruption.

e) Is a congenital anomaly/birth defect

f) Other situations:

- Medical or scientific judgment should be exercised by the Investigator in deciding whether SAE reporting is appropriate in other situations such as significant medical events that may jeopardize the participant or may require medical or surgical intervention to prevent one of the other outcomes listed in the above definition. These events should usually be considered serious.

Note: The following list of medically important events is intended to serve as a guideline for determining which condition has to be considered as a medically important event. The list is not intended to be exhaustive:

- Intensive treatment in an emergency room or at home for:
 - o Allergic bronchospasm
 - o Blood dyscrasias (ie, agranulocytosis, aplastic anemia, bone marrow aplasia, myelodysplasia, pancytopenia, etc.)
 - o Convulsions (seizures, epilepsy, epileptic fit, absence, etc.).
- Development of drug dependence or drug abuse
- ALT $>3 \times$ ULN + total bilirubin $>2 \times$ ULN or asymptomatic ALT increase $>10 \times$ ULN
- Suicide attempt or any event suggestive of suicidality
- Syncope, loss of consciousness (except if documented as a consequence of blood sampling)
- Bullous cutaneous eruptions

- Chronic neurodegenerative diseases (newly diagnosed) or aggravated during the study

